Serious and nonserious AE monitoring	X	→	→	→	→	→	→	X	X		See Section 8.4.3 for follow-up AE and SAE assessments.
Physical examination	X	X					X			X	Complete PE at screening or upon admission for a participant's first period in the study. Otherwise, brief PE performed for findings during previous exam or new/open AEs, at investigator discretion. See Section 8.3.1 for additional details.
Neurological examination		X		X			X			X	Additional exams performed at investigator discretion. See Section 8.3.2 for additional details.
Respiratory rate				X			X				
Supine BP and pulse rate	X			X	X	X	X	X		X	Single supine blood pressure and pulse rate at screening, follow-up visit, and ET. Triplicate supine blood pressure and pulse rate at all other times. See Section 8.3.3 for additional details.
12-Lead ECG	X			X	X	X	X	X		X	Single 12-lead ECG at screening, follow-up visit, and ET. Triplicates at all other times. See Section 8.3.4 for additional details.
Continuous cardiac telemetry		X									Baseline telemetry to be recorded for at least 2 hours prior to the first dose in Period 1 only. This may be done immediately prior to dosing or at some 2-hour continuous interval in the 24 hours prior to dosing, as long as the participant is awake. Post-dose telemetry will continue for 8 hours after dosing. See Section 8.3.4.1 for additional details.
Blinded study intervention administration											
Standardized meals/snack		X		X	→	→	X				See Section 5.3.2 .
Blood samples for:											
Clinical safety lab tests, including lipid panel	X	X		X			X	X		X	Participants to fast for at least 10 hours prior to sample collection for clinical safety lab tests. See Section 5.3.2 for additional details. Day -1 results will be reviewed and confirmed acceptable prior to dosing.
Serum FSH	X										Only for postmenopausal women.

Table 1. Study Schedule of Assessments

Visit Identifier Abbreviations used in this table are in Appendix 10 .	Screen	Period 1 to Period 4						Follow-Up		ET	Notes
Days Relative to Day 1	Day -28 to Day -2	Day -1	Day 1	Day 2	Day 3	Day 4	Visit: Day 8-11	Contact: Day 29-36			Follow-up contact may occur via telephone contact and must occur 28-35 days after the final dose of study intervention.
Hours After Dose			0	24	36	48	72				
HBcAb, HBsAg, HCVAb, HIV testing	X										See Appendix 2 : Clinical Laboratory Tests.

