7.1.2. ECG Changes

A participant who meets either of the following bulleted criteria based on the average of triplicate ECG readings will be withdrawn from the study intervention.

- QTcF >500 msec.
- Change in QTcF from baseline >60 msec and QTcF >450 msec.

If a clinically significant finding is identified (including, but not limited to, changes from baseline in QTcF after enrollment), the investigator or qualified designee will determine if the participant can continue in the study and if any change in participant management is needed. This review of the ECG printed at the time of collection must be documented. Any new clinically relevant finding should be reported as an AE.

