8.3.4. Electrocardiograms

Standard 12-lead ECGs will be collected at times specified in the [SoA](#) section of this protocol using an ECG system that automatically calculates the HR and measures PR, QT, QTcF, and QRS intervals. All scheduled ECGs should be performed after the participant has rested quietly for at least 5 minutes in a supine position.

Triplicate 12-lead ECGs will be obtained approximately 2-4 minutes apart; the average of the triplicate ECG measurements collected at -1.0, -0.5, and 0 hours pre-dose on Day 1 of each period will serve as each participant's baseline QTcF value for that period.

To ensure safety of the participants, a qualified individual at the investigator site will make comparisons to baseline measurements from the current period. Additional ECG monitoring will occur if a) the mean value from the triplicate measurements for any post-dose QTcF interval is increased by ≥ 60 ms from the baseline **and** is > 450 ms; or b) an absolute QT value is ≥ 500 ms for any scheduled ECG. If either of these conditions occurs, then a single ECG measurement must be repeated at least hourly until QTcF values from 2 successive ECGs fall below the threshold value that triggered the repeat measurement.

For single ECG collections, additional ECG monitoring will occur if a) a postdose QTcF interval is increased by ≥ 60 ms from the baseline **and** is > 450 ms; or b) an absolute QT value is ≥ 500 ms for any scheduled ECG. If either of these conditions occurs, then 2 additional ECGs will be collected approximately 2 to 4 minutes apart to confirm the original measurement. If the QTcF values from these repeated ECGs remain above the threshold value, then a single ECG must be repeated at least hourly until QTc values from 2 successive ECGs fall below the threshold value that triggered the repeat measurement.

If a) a postdose QTcF interval remains ≥ 60 ms from the baseline **and** is > 450 ms; or b) an absolute QT value is ≥ 500 ms for any scheduled ECG for greater than 4 hours (or sooner, at the discretion of the investigator); or c) QTcF value get progressively longer, the participant should undergo continuous ECG monitoring. A cardiologist should be consulted if QTcF

values do not return to less than the criteria listed above after 8 hours of monitoring (or sooner, at the discretion of the investigator).

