In some cases, it may be appropriate to repeat abnormal ECGs to rule out improper lead placement as contributing to the ECG abnormality. It is important that leads be placed in the same positions each time in order to achieve precise ECG recordings. If a machine-read QTc value is prolonged, as defined above, repeat measurements may not be necessary if a qualified medical provider's interpretation determines that the QTcF values are in the acceptable range.

ECG values of potential clinical concern are listed in [Appendix 8](#).

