10.8. Appendix 8: ECG Findings of Potential Clinical Concern

ECG Findings That May Qualify as AEs

Marked sinus bradycardia (rate <40 bpm) lasting minutes.New PR interval prolongation >280 ms.New prolongation of QTcF to >480 ms (absolute).New prolongation of QTcF by >60 ms from baseline.New-onset atrial flutter or fibrillation, with controlled ventricular response rate: ie, rate <120 bpm.New-onset type I second-degree (Wenckebach) AV block of >30-second duration.Frequent PVCs, triplets, or short intervals (<30 seconds) of consecutive ventricular complexes.
ECG Findings That May Qualify as SAEs

QTcF prolongation >500 ms.Absolute value of QTcF > 450 ms AND QTcF change from baseline >60 ms.New ST-T changes suggestive of myocardial ischemia.New-onset LBBB (QRS complex >120 ms).New-onset right bundle branch block (QRS complex >120 ms).Symptomatic bradycardia.Asystole
In awake, symptom-free participants in sinus rhythm, with documented asystolic pauses ≥ 3 seconds or any escape rate <40 bpm, or with an escape rhythm that is below the AV node;In awake, symptom-free participants with atrial fibrillation and bradycardia with 1 or more asystolic pauses of at least 5 seconds or longer.Atrial flutter or fibrillation, with rapid ventricular response rate: rapid = rate >120 bpm.

- Sustained supraventricular tachycardia (rate >120 bpm) (“sustained” = short duration with relevant symptoms or lasting >1 minute).
- Ventricular rhythms >30 seconds’ duration, including idioventricular rhythm (HR <40 bpm), accelerated idioventricular rhythm (HR >40 bpm to <100 bpm), and monomorphic/polymorphic ventricular tachycardia (HR >100 bpm [such as torsades de pointes]).
- Type II second-degree (Mobitz II) AV block.
- Complete (third-degree) heart block.

ECG Findings That Qualify as SAEs

- Change in pattern suggestive of new myocardial infarction.
- Sustained ventricular tachyarrhythmias (>30-seconds duration).
- Second- or third-degree AV block requiring pacemaker placement.
- Asystolic pauses requiring pacemaker placement.
- Atrial flutter or fibrillation with rapid ventricular response requiring cardioversion.
- Ventricular fibrillation/flutter.
- At the discretion of the investigator, any arrhythmia classified as an adverse experience.

[figure not shown]

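### The absolute repeat-ECG trigger in Protocol 8.3.4 is set on uncorrected QT, so a QTcF above 500 ms that requires withdrawal under 7.1.2 can, in a narrow zone, call for no mandatory hourly repeats

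*Protocol*

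**What the plan says.** Protocol 8.3.4 gives the trigger three times: for triplicate ECGs, for single ECGs, and for the step to continuous ECG monitoring when the condition lasts more than 4 hours. Each statement has the same two limbs:

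- Limb (a): QTcF has risen by at least 60 ms from the period baseline and is above 450 ms. Both parts are needed.
- Limb (b): "an absolute QT value is ≥ 500 ms for any scheduled ECG".

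The continuous-monitoring paragraph adds a third limb, on trend: "QTcF value get progressively longer, the participant should undergo continuous ECG monitoring".

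What happens after a trigger is written on QTcF. Hourly repeats for triplicates run "until QTcF values from 2 successive ECGs fall below the threshold value that triggered the repeat measurement". For single ECGs, confirmation starts "If the QTcF values from these repeated ECGs remain above the threshold value". The section ends by allowing repeats to be skipped if a qualified provider's "interpretation determines that the QTcF values are in the acceptable range".

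Elsewhere the 500 ms line is on QTcF. Section 7.1.2 withdraws a participant from study intervention, on the triplicate mean, for "QTcF >500 msec", with no condition on change from baseline. Appendix 8 lists "QTcF prolongation >500 ms" among findings that may qualify as SAEs.

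**The concern.** A value that ends a participant's dosing should also, one would expect, start the protocol's own repeat-ECG procedure. As written it need not, because neither entry limb is a stand-alone QTcF limit. If the value then stays stable, the 4-hour step to continuous monitoring is not reached either: that step reuses (a) and (b), and its third limb needs progressive lengthening.

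There is a second defect, which does not depend on the narrow zone. When limb (b) does fire, confirmation and exit compare QTcF with the threshold that triggered the repeat, but limb (b) contains no QTcF threshold. The site must guess the number.

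At stake is the clarity of a real-time safety rule in a first-in-human study. Withdrawal does not replace the repeats, because each period is a single dose (Protocol 4.1): it prevents later doses but does not follow the current exposure. No endpoint, analysis or sample-size consideration is affected.

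**Working it through.** **Inputs**

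- Limbs (a) and (b): Protocol 8.3.4.
- Withdrawal at mean QTcF >500 ms: Protocol 7.1.2.
- Screening limit of 450 ms for QTcF: Protocol 5.2, criterion 10.
- Period baseline: mean of the triplicates at -1, -0.5 and 0 h in each period (Protocol 8.3.4, SAP 3.1.4).
- Correction: QTcF = QT/RR^(1/3), with RR = 60/HR (SAP 3.1.4). Hence QT = QTcF × (60/HR)^(1/3).

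**Is QT here shorthand for QTcF?** Section 8.3.4 lists QT and QTcF as separate measurements, and Protocol 9.3.1.1 tabulates uncorrected QT above 500 ms separately from the QTcF categories. The literal reading is therefore uncorrected QT.

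**When does QTcF >500 ms fire neither limb?**

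- Limb (a) fails if QTcF < baseline + 60. With QTcF >500, that needs baseline >440 ms.
- Limb (b) fails if QT <500, that is, QTcF < 500 × (HR/60)^(1/3). With QTcF >500, that needs HR >60 bpm.

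The zone is therefore 500 < QTcF < min(baseline + 60, 500 × (HR/60)^(1/3)).

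**Width set by baseline.** The heart rate needed for full width w is 60 × ((500 + w)/500)³.

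| Period baseline (ms) | Zone for QTcF (ms) | Width (ms) | HR for full width (bpm) |
|---|---|---|---|
| 440 | none | 0 | n/a |
| 441 | 500–501 | 1 | 60.4 |
| 445 | 500–505 | 5 | 61.8 |
| 448 | 500–508 | 8 | 62.9 |
| 450 | 500–510 | 10 | 63.7 |

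**Width set by heart rate, at baseline 450.** 500 × (HR/60)^(1/3) is 502.8 at 61 bpm, 505.5 at 62 and 508.2 at 63, so the widths are 2.8, 5.5 and 8.2 ms. At 64 bpm it is 510.9, and the baseline limit of 510 takes over.

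**Example.** Baseline 448 ms, post-dose mean QTcF 505 ms, heart rate 75 bpm.

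- Rise: 505 − 448 = 57 ms, below 60, so (a) is not met.
- QT: 505 × (60/75)^(1/3) = 468.8 ms, below 500, so (b) is not met.
- QTcF 505 > 500, so 7.1.2 requires withdrawal.

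At 60 bpm the same QTcF gives QT 505 ms, and (b) fires.

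**The missing threshold.** QT 500 ms at 45 bpm corresponds to QTcF 500/(60/45)^(1/3) = 454.3 ms. Limb (b) fires there. If the threshold is taken to be QTcF 500 ms, the participant was already below it when the trigger fired. If it is not, the protocol gives no QTcF number to compare with.

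**After the fix.** If limb (b) also fires at QTcF ≥500 ms, every value above 500 ms triggers repeats, and the zone is empty at any baseline and heart rate.

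**The case against.** The strongest reply is that little is lost. Scheduled triplicate ECGs continue on Day 1 and at 24, 36, 48 and 72 h (Protocol 1.3), with the participant in the unit through at least 72 h (4.1). "Post-dose telemetry will continue for 8 hours after dosing". Section 7.1.2 has the investigator decide on continuation and management after a clinically significant finding, with the ECG review documented. Sections 8.4.3 and 10.3.3 oblige the investigator to follow each adverse event and to arrange medically indicated measurements. An SAE on active treatment pauses dosing (6.6.1). All of this stands. A reader might infer that a participant in the zone would have no required repeat ECG or would go unfollowed, and the documents do not support that. None of these provisions sets an hourly cadence, and that is all that is missing.

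A second reply is that limb (b) was probably meant as QTcF, since confirmation and exit are on QTcF. That may be so, and the zone then disappears. But the text says QT in all three places, and the protocol elsewhere treats uncorrected QT as its own quantity. The correction is worth making on either view.

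Third, limb (b) refers to any scheduled ECG, so a per-tracing reading would let one tracing fire it. That helps near the edge: at 62 bpm and QTcF 505 ms, QT is 499.5 ms. In the 75 bpm example a tracing would have to exceed the mean by about 31 ms (500 − 468.8).

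Two further inferences should be resisted. One is a specific number of unmonitored hours between the last Day 1 ECG and the 24 h ECG: column alignment in the available copy of Table 2 is uncertain, so that interval should not be relied on. The other is that leaving the repeats on QTcF is wrong: the section itself makes QTcF decisive for whether repeats are needed, and that is reasonable.

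**Conclusion.** The point holds and is minor. On the literal text, a mean QTcF above 500 ms that requires withdrawal under 7.1.2 does not trigger the mandatory hourly repeats when the period baseline is above 440 ms, the rise is below 60 ms and heart rate is above about 60 bpm. If it is stable, it does not trigger the 4-hour step to continuous monitoring either. Separately, limb (b) leaves the confirmation and exit threshold undefined.

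The maximum width of 10 ms assumes that the period baseline is at or below the 450 ms screening limit. The protocol sets no ceiling on later period baselines. If one were 455 or 460 ms, the same formula gives 15 or 20 ms (at heart rates of at least 65.6 or 67.5 bpm), but nothing in the documents indicates that this will happen. Nor do they give a basis for how often any participant would fall in the zone. Confidence is high for the text and the arithmetic. What the authors intended is open.

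**What to change.** In Protocol 8.3.4:

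1. In all three (b) clauses, write 'QT or QTcF ≥500 ms'. Adding QTcF is preferable to replacing QT, because 9.3.1.1 already reports uncorrected QT above 500 ms.
2. State that the confirmation and exit threshold for limb (b) is QTcF 500 ms.
3. Keep the exit on QTcF. An exit on uncorrected QT could hold a participant with slow heart rate and acceptable QTcF in hourly repeats: QTcF 450 ms at 43 bpm gives QT 450 × (60/43)^(1/3) = 502.9 ms.

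The cost is wording in one section, using a value the ECG system already calculates. In conduct it means at most a few extra ECGs, and continuous monitoring if QTcF stays at or above 500 ms for more than 4 hours.

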8.3.4.1. Continuous Cardiac Monitoring by Telemetry

All abnormal rhythms will be recorded and reviewed by the study physician for the presence of rhythms of potential clinical concern. The time, duration, and description of the clinically significant event will be recorded in the CRF. In addition, a printed record of the tracing(s) of the clinically significant rhythm(s) will be made and retained with other source documents.

Telemetry should be collected using a centralized system that also allows for the storage and advanced analysis of all recorded data in order to preserve important events for future evaluations. Holter monitoring should not be used in parallel with continuous telemetry, unless it is the only means of data storage available at the investigator site, or verifiable arrhythmia quantification is required. To establish a baseline, telemetry should be recorded for at least 2 hours before dosing in Period 1. This may be done immediately prior to dosing or at some 2-hour continuous interval in the 24 hours prior to dosing, as long as the recording is performed when the participant is awake. Telemetry may be stopped within a reasonably short period of time prior to dosing, in order to avoid interference with study operations conducted immediately before dosing. However, it is expected that the telemetry leads will be in place and the system connected prior to dosing.

8.3.5. Clinical Safety Laboratory Assessments

See [Appendix 2](#) for the list of clinical safety laboratory tests to be performed and the [SoA](#) for the timing and frequency. All protocol-required laboratory assessments, as defined in [Appendix 2](#), must be conducted in accordance with the laboratory manual and the [SoA](#). Unscheduled clinical laboratory measurements may be obtained at any time during the study to assess any perceived safety issues.

The investigator must review the laboratory report, document this review, and record any clinically significant changes occurring during the study in the AE section of the CRF. Clinically significant abnormal laboratory test findings are those that are not associated with the underlying disease, unless judged by the investigator to be more severe than expected for the participant's condition.

All laboratory tests with values considered clinically significant and abnormal during participation in the study or within 14 days after the last dose of study intervention should be

repeated until the values return to normal or baseline or are no longer considered clinically significant by the investigator or study medical monitor.

If such values do not return to normal/baseline within a period of time judged reasonable by the investigator, the etiology should be identified and the sponsor notified.

See [Appendix 6](#) for suggested actions and follow-up assessments in the event of potential DILI.

See [Appendix 7](#) for instructions for laboratory testing to monitor kidney function and reporting laboratory test abnormalities.

Participants may undergo random urine drug testing at the discretion of the investigator. Drug testing conducted prior to dosing must be negative for participants to receive study intervention.

8.4. Adverse Events, Serious Adverse Events, and Other Safety Reporting

The definitions of an AE and an SAE can be found in [Appendix 3](#).

AEs may arise from symptoms or other complaints reported to the investigator by the participant (or, when appropriate, by a caregiver, surrogate, or the participant's legally authorized representative), or they may arise from clinical findings of the investigator or other healthcare providers (clinical signs, test results, etc).

The investigator and any qualified designees are responsible for detecting, documenting, and recording events that meet the definition of an AE or SAE and remain responsible to pursue and obtain adequate information both to determine the outcome and to assess whether the event meets the criteria for classification as an SAE or caused the participant to discontinue the study intervention (see [Section 7.1](#)).

During the active collection period as described in Section 8.4.1, each participant will be questioned about the occurrence of AEs in a nonleading manner.

In addition, the investigator may be requested by Pfizer Safety to obtain specific follow-up information in an expedited fashion.

8.4.1. Time Period and Frequency for Collecting AE and SAE Information

The time period for actively eliciting and collecting AEs and SAEs ("active collection period") for each participant begins from the time the participant provides informed consent, which is obtained before undergoing any study-related procedure and/or receiving study intervention), through and including a minimum of 28 calendar days, except as indicated below, after the last administration of the study intervention.

Follow-up by the investigator continues throughout the active collection period and until the AE or SAE or its sequelae resolve or stabilize at a level acceptable to the investigator.

When a clinically important AE remains ongoing at the end of the active collection period, follow-up by the investigator continues until the AE or SAE or its sequelae resolve or stabilize at a level acceptable to the investigator and Pfizer concurs with that assessment.

For participants who are screen failures, the active collection period ends when screen failure status is determined.

If the participant withdraws from the study and also withdraws consent for the collection of future information, the active collection period ends when consent is withdrawn.

If a participant permanently discontinues or temporarily discontinues study intervention because of an AE or SAE, the AE or SAE must be recorded on the CRF and the SAE reported using the CT SAE Report Form.

Investigators are not obligated to actively seek information on AEs or SAEs after the participant has concluded study participation. However, if the investigator learns of any SAE, including a death, at any time after a participant has concluded study participation, and they consider the event to be reasonably related to the study intervention, the investigator must promptly report the SAE to Pfizer using the CT SAE Report Form.

8.4.1.1. Reporting SAEs to Pfizer Safety

All SAEs occurring in a participant during the active collection period as described in [Section 8.4.1](#) are reported to Pfizer Safety on the CT SAE Report Form immediately upon awareness and under no circumstance should this exceed 24 hours, as indicated in [Appendix 3](#). The investigator will submit any updated SAE data to the sponsor within 24 hours of its being available.

8.4.1.2. Recording Nonserious AEs and SAEs on the CRF

All nonserious AEs and SAEs occurring in a participant during the active collection period, which begins after obtaining informed consent as described in [Section 8.4.1](#), will be recorded on the AE section of the CRF.

The investigator is to record on the CRF all directly observed and all spontaneously reported AEs and SAEs reported by the participant.

As part of ongoing safety reviews conducted by the sponsor, any nonserious AE that is determined by the sponsor to be serious will be reported by the sponsor as an SAE. To assist in the determination of case seriousness, further information may be requested from the investigator to provide clarity and understanding of the event in the context of the clinical study.

Reporting of AEs and SAEs for participants who fail screening are subject to the CRF requirements as described in [Section 5.4](#).

